### **10.2.2 Renal safety monitoring**

The following two categories of abnormal renal laboratory values have to be considered during the course of the study:

- Serum creatinine increase  $\geq 25\%$  compared to baseline during normal hydration status
- Urine protein-creatinine ratio (PCR)  $\geq 1\text{g/g}$  or  $\geq 100\text{ mg/mmol}$ , OR new onset dipstick proteinuria  $\geq 3+$  OR new onset dipstick hematuria  $\geq 3+$  (after excluding menstruation, UTI, extreme exercise, or trauma)

Renal event findings must be confirmed 24-48 hours after the first assessment.

Every renal laboratory trigger or renal event as defined in [Table 16-3](#) should be followed up by the investigator or designated personnel at the trial site as summarized in [Section 16.2](#).

Refer to the SOM for additional details.

### **10.2.3 Prospective suicidality assessment**

The Sheehan Suicidality Tracking Scale is a sensitive psychometric tool to prospectively assess for treatment-emergent suicidal thoughts and behaviors. The Sheehan Suicidality Tracking Scale (Sheehan-STS) is a prospective rating scale that tracks both treatment-emergent suicidal ideation and behaviors. The Sheehan-STS is a fourteen-item (up to 22) scale that will be administered by a clinician. Each item in the Sheehan-STS is scored on a 5-point Likert scale

(0=not at all, 1=a little, 2=moderately, 3=very, and 4=extremely). Data from the Sheehan-STS can be analyzed as individual item scores, suicidal ideation subscale score (sum of scores from items 2, 3, and 4, plus score from item 5 if  $\leq 1$ ), suicidal behavior subscale score (sum of scores from items 6, 7a, and 8, plus score from item 5 if  $> 1$ ), and total score.

#### **10.2.4 Data Monitoring Committee**

Not required.

## **11 Data Collection and Database management**

### **11.1 Data collection**

Designated investigator staff will enter the data required by the protocol into the Electronic Case Report Forms (eCRF). The eCRFs have been built using fully validated secure web-enabled software that conforms to 21 CFR Part 11 requirements, Investigator site staff will not be given access to the EDC system until they have been trained. Automatic validation programs check for data discrepancies in the eCRFs and allow modification and/or verification of the entered data by the investigator staff.

The investigator/designee is responsible for assuring that the data (recorded on CRFs) (entered into eCRF) is complete, accurate, and that entry and updates are performed in a timely manner. The Investigator must certify that the data entered are complete and accurate

After final database lock, the investigator will receive copies of the subject data for archiving at the investigational site.

All data should be recorded, handled and stored in a way that allows its accurate reporting, interpretation and verification.

### **11.2 Database management and quality control**

Novartis personnel (or designated CRO) will review the data entered by investigational staff for completeness and accuracy. Electronic data queries stating the nature of the problem and requesting clarification will be created for discrepancies and missing values and sent to the investigational site via the EDC system. Designated investigator site staff are required to respond promptly to queries and to make any necessary changes to the data.

Concomitant treatments and prior medications entered into the database will be coded using the WHO Drug Reference List, which employs the Anatomical Therapeutic Chemical classification system. Medical history/current medical conditions and adverse events will be coded using the Medical dictionary for regulatory activities (MedDRA) terminology.

Randomization codes and data about all study treatment (s) dispensed to the subject and all dosage changes will be tracked using the Novartis Interactive Response Technology (NIRT).

Each occurrence of a code break via NIRT will be reported to the clinical team and monitor. The code break functionality will remain available until study shut down or upon request of Novartis.

Once all the necessary actions have been completed and the database has been declared to be complete and accurate, it will be locked and the treatment codes will be unblinded and made available for data analysis. Any changes to the database after that time can only be made after written agreement by Novartis development management.

Commercially Confidential Information

### **11.3 Site monitoring**

Before study initiation, at a site initiation visit or at an investigator's meeting, a Novartis/delegated CRO representative will review the protocol and data capture requirements (i.e. eSource DDE or eCRFs) with the investigators and their staff. During the study, Novartis employs several methods of ensuring protocol and GCP compliance and the quality/integrity of the sites' data. The field monitor will visit the site to check the completeness of subject records, the accuracy of data capture / data entry, the adherence to the protocol and to Good Clinical Practice, the progress of enrollment, and to ensure that study treatment is being stored, dispensed, and accounted for according to specifications. Key study personnel must be available to assist the field monitor during these visits. Continuous remote monitoring of each site's data may be performed by a centralized Novartis/delegated CRO/CRA organization. Additionally, a central analytics organization may analyze data & identify risks & trends for site operational parameters, and provide reports to Novartis clinical teams to assist with trial oversight.

The investigator must maintain source documents for each subject in the study, consisting of case and visit notes (hospital or clinic medical records) containing demographic and medical information, laboratory data, electrocardiograms, and the results of any other tests or assessments. All information on CRFs must be traceable to these source documents in the subject's file. The investigator must also keep the original informed consent form signed by the subject (a signed copy is given to the subject).

The investigator must give the monitor access to all relevant source documents to confirm their consistency with the data capture and/or data entry. Novartis monitoring standards require full verification for the presence of informed consent, adherence to the inclusion/exclusion criteria, documentation of SAEs, and of data that will be used for all primary variables. Additional checks of the consistency of the source data with the CRFs are performed according to the study-specific monitoring plan. No information in source documents about the identity of the subjects will be disclosed.

## **12 Data analysis and statistical methods**

The analysis will be conducted on all subject data at the time the trial ends. Any data analysis carried out independently by the investigator should be submitted to Novartis before publication or presentation.

### **12.1 Analysis sets**

Commercially Confidential Information

### **12.2 Subject demographics and other baseline characteristics**

Demographic and other baseline data including disease characteristics will be listed and summarized descriptively by treatment group for the FAS and the safety analysis set.

Categorical data will be presented as frequencies and percentages. For continuous data, mean, standard deviation, median, minimum, and maximum will be presented. For selected parameters, 25th and 75th percentiles will also be presented.

Relevant medical histories and current medical conditions at baseline will be summarized by system organ class and preferred term, by treatment group.

### **12.3 Treatments**

Data for study drug administration and concomitant therapies will be summarized by treatment group.

Total duration of time on study drug and reasons for discontinuation of study drug will be summarized by treatment group.

All available data under safety analysis set will be used for reporting purpose.

### **12.4 Analysis of the primary endpoint(s)**

The primary aim of this study is to determine whether MIJ821 displays clinical efficacy and safety to support further development for treatment-resistant depression.

#### **12.4.1 Definition of primary endpoint(s)**

The primary efficacy endpoint is change from baseline in the total MADRS score at 24 h after single dose administration. The primary analysis will be performed on the ITT set. In addition, a similar analysis will be performed on the PPS.

The primary efficacy analysis may be performed once the 24-hour outcome data on MADRS score are available from all study participants. These results may help facilitate further planning activities within the MIJ821 program.

#### **12.4.2 Statistical model, hypothesis, and method of analysis**

The change from baseline in the total MADRS score at 24 hours after single dose administration will be analyzed using an analysis of covariance (ANCOVA) model with treatment as a group factor and baseline MADRS score as a covariate.

Commercially Confidential Information

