### **3 Study design**

This is a non-confirmatory, multi-center, 6-treatment arm in the European countries and 5-treatment arm in the USA (no ketamine arm), randomized, subject and investigator blinded, parallel group, placebo controlled study in treatment-resistant depression patients. The study will randomize approximately 66 Subjects and while the study design utilizes an outpatient visit schedule, the study allows for the inclusion of subjects seeking treatment for their disease from both an 'inpatient' or 'outpatient' clinic setting.

A screening period of maximum 4 weeks will be used to assess eligibility. Patients who meet the eligibility criteria at screening will proceed to baseline evaluations on Day-1 or Day 1. All baseline safety evaluation results must be available prior to randomization. At the baseline visit, eligible subjects will be randomized to one of the treatment arms. Randomized subjects will enter a 36- day treatment period, receiving at each treatment visit, a 40-minute infusion with a safety observation period of 2-4 hours (i.e. a minimum of 2 hours) post the start of

infusion. If the subject reports no dissociative symptoms and no suicidal symptoms, the subject will be allowed to leave the clinical treatment setting. Visits to assess efficacy and safety are scheduled at 24 hours, 48 hours (if applicable) and every week during the treatment period. If 48 hour visit (V103) is conducted, then all assessments should be completed. The assessment to address the primary objective will be performed at 24 hour post-dose. Safety assessments will include physical examinations, ECGs, vital signs, standard clinical laboratory evaluations (hematology, blood chemistry, and urinalysis), adverse event and serious adverse event monitoring. At the conclusion of the treatment period (Day 1 - Day 36), subjects will enter a 5-week follow up period consisting of two follow visits approximately 1 week (Day 43) and 3 weeks (Day 57) after the last study drug administration and an end of study completion visit (Day 71) The total duration for each subject in the study is maximum 14-weeks including screening and baseline. No interim analysis is planned. The study design is summarized in [Figure 3-1](#) below for the European countries (same study design without the ketamine arm in the USA).

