### **4.3 Rationale for choice of control drugs (comparator/placebo) or combination drugs**

The use of placebo saline solution is to provide a comparison group for an unbiased collection and assessment of safety and tolerability data.

Ketamine is included primarily for assay sensitivity and for comparison of side effects. Ketamine is known to be effective with large effect sizes for severe depressive episodes, and it also has high rates of dissociative side effects in 20-30% of subjects, often of moderate to marked severity. It also can cause manic episodes, mixed states, and suicidal or aggressive reactions in a small minority of persons. A single subanesthetic dose of intravenous ketamine consistently decreases symptoms of depression in subjects with treatment-resistant depression in a rapid (within hours), robust (across many symptoms of depression) and relatively sustained (typically, 7–14 days) manner ([Berman et al 2000](#); [Cusin et al 2017](#)). Repeated doses (six infusions over the course of several weeks) have shown promise from an efficacy and safety standpoint ([Aan het Rot et al 2010](#)). The efficacy of two times versus three times a week intravenous ketamine in subjects with treatment-resistant depression in sustaining the initial antidepressant effects was evaluated. Both doses (0.5 and 0.75 mg/kg) were significantly superior to placebo in treating depression symptoms and the transient dissociative side effects attenuated with repeat dosing ([Singh et al 2016](#)). One study examined the benefits of a fixed course of 4 once-weekly ketamine sessions (0.5 mg/kg IV) as continuation phase treatment in 5 patients who had remitted after acute phase treatment. All 5 patients maintained improvement during the continuation phase ([Krystal et al 1994](#)).

To limit any dissociative and psychomimetic side effects, the limiting dose for Ketamine infusion is at 40 mg/infusion for patients over 80 kg.

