## 5 Population

Approximately 66 subjects (66 completers for the primary endpoint) diagnosed with treatment-resistant depression will be randomized to:

Commercially Confidential Information

In the USA, no ketamine arm will be included.

It will be competitive recruitment per region.

The investigator or designee must ensure that all subjects being considered for the study meet the following eligibility criteria.

Subject selection is to be established by checking through all eligibility criteria at screening. A relevant record (e.g. checklist) of the eligibility criteria must be stored with the source documentation at the study site.

Deviation from any of the entry criterion excludes a subject from enrollment into the study.

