#### 6.1.3 Treatment arms/group

Subjects will be assigned at the baseline to one of the following 6-treatment arms in the European countries (5-treatment arms in the USA) in a ratio defined on the [Section 5](#).

Commercially Confidential Information

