#### **6.3.2 Treatment assignment, randomization**

The randomization numbers will be generated using the following procedure to ensure that treatment assignment is unbiased and concealed from subjects and investigator staff. A subject randomization list will be produced by the IRT provider, or by a delegate under Novartis supervision, using a validated system that automates the random assignment of subject numbers to randomization numbers. These randomization numbers are linked to the different treatment arms.

Randomization will be stratified by region, US and European countries.

The randomization scheme for subjects will be reviewed and approved by a member of the Randomization Office.

Follow the details outlined in the SOM regarding the process and timing of treatment assignment and randomization of subjects.

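### The primary ANCOVA as stated leaves out region, the stratification factor: a small precision loss for MIJ821 versus placebo, and a possible bias in any ketamine contrast that pools regions

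*Protocol*

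**What the plan says.** Two visible statements define the primary model, in Protocol Section 12.4.2 and in the Data analysis row of the synopsis. Both describe an "analysis of covariance (ANCOVA) model with treatment as a group factor and baseline MADRS score as a covariate", and neither names region.

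Other sections make region part of the design:
- Section 6.3.2: "Randomization will be stratified by region, US and European countries".
- Section 5: "In the USA, no ketamine arm will be included". Sections 3 and 6.1.3 agree, with six arms in Europe and five in the US.
- Section 5 also says: "It will be competitive recruitment per region". No visible text fixes the US share.

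Section 12.4 gives the primary aim as to "determine whether MIJ821 displays clinical efficacy and safety to support further development". On the active comparator, Section 4.3 says: "Ketamine is included primarily for assay sensitivity and for comparison of side effects".

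The rest of 12.4.2, the sensitivity and supportive analyses (12.4.4), the sample size (12.8.1), and SAP 6.1.3 to 6.1.5 and 6.2.3.1 are redacted.

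**The concern.** Leaving a stratification factor out of the model usually costs only efficiency, because every arm has the same mix of strata. That holds here for MIJ821 against placebo. It does not hold for ketamine: its arm contains no US subjects, while the other five arms can contain both regions. Randomisation cannot balance this, because a US subject cannot be assigned to ketamine.

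Under the stated model a ketamine contrast therefore sets a European mean against mixed-region means. Baseline MADRS removes only the part of a regional difference that baseline explains. If assay sensitivity were judged from such a contrast, a remaining regional difference in 24-hour change could make ketamine look better or worse than it is. The direction is unknown.

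**Working it through.** **Inputs.** From the documents: the model terms, the stratification factor, five arms recruiting in both regions plus ketamine in Europe only, and about 66 subjects. The visible text gives no SD, alpha, allocation ratio, US share or regional difference, so there is no plan figure to reproduce. Assumed: residual SD σ = 10 MADRS points; two-sided 5% test; no treatment effect; total N 64 to 66; US share p of each non-ketamine arm 18 to 67%; residual US–Europe difference D of 0 to 6 points. Simulations used 40,000 trials per cell, with baseline SD 5 and slope −0.5.

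**1. MIJ821 versus placebo.** Bias = (difference in US share between the two arms) × D. This is zero if the ratio is the same in both regions. If the shares differed by 0.10, it would be 0.10 × 2 = 0.2 to 0.10 × 5 = 0.5 points for D = 2 to 5.

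Standard error, 6 European and 6 US subjects per arm, 6 ketamine, D = 6:
- With region: 10 × √(1/12 + 1/12) = 4.08.
- Without region, the residual variance rises by 60 × 0.25 × 36 / 59 = 9.2, so SE = √109.2 × √(2/12) = 4.27, about 4.5% wider.
- Simulated: 4.28 without against 4.10 with; rejection 3.9% against 4.8%.

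The approximation √(1 + p(1 − p)(D/σ)²) gives 0.3 to 0.5% at D = 2, 0.7 to 1.1% at D = 3 and 2.0 to 3.1% at D = 5 (p = 0.20 to 0.50). The estimate itself barely varies more; the test is slightly conservative.

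**2. Ketamine versus placebo, pooled, without region.** Absolute bias = p × D. With p from 2/11 to 8/12, this is 0.36 to 1.33 points at D = 2, 0.91 to 3.33 at D = 5 and 1.09 to 4.00 at D = 6. In SE units these are 0.08 to 0.30, 0.20 to 0.73 and 0.24 to 0.86. Simulated false-positive rates (%):

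| Ketamine n | Europe/US per other arm | D = 0 | D = 2 | D = 5 | D = 6 |
|---|---|---|---|---|---|
| 11 | 9/2 | 5.0 | 4.9 | 5.2 | 5.2 |
| 11 | 7/4 | 5.1 | 5.4 | 6.4 | 6.7 |
| 11 | 5/6 | 5.0 | 5.7 | 8.7 | 10.2 |
| 11 | 4/7 | 4.8 | 5.8 | 10.2 | 12.4 |
| 9 | 9/2 | 4.9 | 5.0 | 5.0 | 5.2 |
| 6 | 6/6 | 5.0 | 5.2 | 7.0 | 7.8 |
| 5 | 5/7 | 5.0 | 5.5 | 7.6 | 8.2 |
| 4 | 4/8 | 5.0 | 5.7 | 8.0 | 9.2 |

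With region in the model, bias is about 0 and the rate is 4.8 to 5.2% in every cell.

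**3. Only the residual difference counts.** With 6/6 per arm, a raw difference of 5 points of which baseline explains 2 gives an error of 0.5 × 5 = 2.5 in raw change but 1.3 in the ANCOVA. That is a little under 0.5 × 3 = 1.5, because without region the baseline slope absorbs part of the difference. If baseline explains all of a 3-point difference, the ANCOVA error is about 0.

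**4. Precision of the ketamine contrast.** With region, SE = σ√(1/n_K + 1/n + (US/Europe)/(5n)), where n_K is the ketamine arm and n each other arm. For 6/6 with 6 ketamine: 10 × √(1/6 + 1/12 + 1/60) = 5.16, against 10 × √(1/6 + 1/12) = 5.00 at the same residual SD without region and 10 × √(1/6 + 1/6) = 5.77 for Europeans only.

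**5. If the regional difference varies by arm.** With 6/6, a difference of 5 in placebo and 2 in the four MIJ821 arms, the estimated region effect averages (5 + 4 × 2)/5 = 2.6. The ketamine–placebo bias is 0.5 × 5 = 2.5 without region, 0.5 × (5 − 2.6) = 1.2 with a region main effect, and 0 in Europeans only.

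**The case against.** **Redaction.** The redacted sections could contain a region term or a European-only ketamine comparison. This stands as a limit. The point rests on two intact sentences that list the model terms; if region appears elsewhere, those sentences are incomplete.

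**No ketamine efficacy contrast is visible.** The primary aim concerns MIJ821, and Section 4.3 does not say how assay sensitivity will be judged. The bias needs a ketamine contrast, pooled over regions, without region, plus a residual regional difference. This also stands: the bias is conditional. Nor does stratification show that region predicts outcome; the different arm sets may be reason enough to randomise by region.

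**The upper rates need an unusual allocation.** Every rate above 10% has 11 ketamine subjects against 4 or 5 Europeans in each other arm. With equal allocation within Europe the maxima are 8.0% at 5 points and 9.2% at 6, and those need 67% US recruitment. At 2 points no layout exceeds 5.8%. Bias stays below one standard error throughout, so sampling error dominates.

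**For the primary question the study is non-confirmatory and the test only mildly conservative.** True, and the weight given to the point should reflect it. None of this argues for leaving out a factor already used to randomise.

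**Conclusion.** The concern holds on the visible text: both statements of the primary model omit region. The validity of MIJ821 versus placebo is not threatened, provided the MIJ821:placebo ratio is the same in both regions; the allocation ratio is redacted. The loss there is a standard error up to about 4.5% too wide at the largest difference considered.

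The more serious consequence is confined to a ketamine contrast that pools regions without adjustment. Its size depends on assumed values of US share, SD, allocation and residual regional difference, and it vanishes if the regions do not differ. It should be fixed because the correction is nearly free, not because harm has been shown. Confidence is medium, given the redactions.

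**What to change.** - Add region (US/Europe) as a fixed factor to the primary ANCOVA in Section 12.4.2 and in the synopsis.
- Make any ketamine efficacy contrast region-adjusted, with a European-only comparison as a sensitivity analysis, because a region main effect assumes that treatment effects do not differ by region.
- If the redacted text already includes region or a European-only ketamine comparison, confirm it and align the two visible statements.
- State whether the redacted efficacy MMRMs include region; no change to them is requested here.

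**Cost.** One phrase in two places and one degree of freedom. At a fixed residual SD, the ketamine–placebo standard error with region rises by 1% (4.26 to 4.31, 18% US) to 8% (4.26 to 4.62, 64% US) with 11 per arm, and by 1 to 5% with equal allocation within Europe. The European-only comparison costs more (5 to 37% and 5 to 22% respectively), which is why it is proposed only as a sensitivity analysis.

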#### **12.4.3 Handling of missing values/censoring/discontinuations**

Commercially Confidential Information

No imputation of missing data will be done for the primary analysis approach.

#### **12.4.4 Sensitivity and Supportive analyses**

##### **Sensitivity analyses**

Commercially Confidential Information

Commercially Confidential Information

